Official Title: The UBC Socializing Together While Running InDEpendently (STRIDE) Pilot  
Trial: A Social Identity Informed Virtual Running Group Program

Protocol ID: H20-03151

NCT ID: Not yet assigned

Last Protocol Update To the University of British Columbia Behavioural Research Ethics Board:  
March 31st, 2021

Protocol Re-Submission Date to clinicaltrials.gov: February 24, 2022

**Rationale:** The current COVID-19 context has resulted in a decrease of physical activity behaviour among Canadian adults (Rhodes et al., 2020). The transition to post secondary education is also associated with decreases in physical activity (Winpenny et al., 2020). With that said, there is a need to support university students' physical activity behaviour, and provide safe opportunities for social interaction, as these are viable coping strategies during the current COVID-19 pandemic (Faulkner et al., 2020). In the proposed randomized controlled pilot trial, the purpose is to examine the feasibility and acceptability of social identity informed virtual running groups to support University of British Columbia (UBC) undergraduate students' well-being. Secondary outcomes include changes in UBC students' exercise identity, perceived social support, exercise behaviour, and well-being. Should the results suggest the intervention is feasible and acceptable, it can inform the development of a larger scale efficacy trial. The pilot intervention can also inform ideal ways to support university students' exercise behaviour and well-being during the pandemic.

Group-mediated interventions (i.e., intervention content is delivered in a social group setting) are a promising approach for promoting health behaviours such as exercise (Beauchamp & Rhodes, 2020). Based on social identity theorising and research, belonging to meaningful groups that with which one positively identifies can support well-being and health (Haslam et al., 2009). Positive group identification refers to individuals integrating a particular group membership (e.g., exercise group) as an important part of their identity, and positively identifying with members, values, and norms of that group. Meta-analytic evidence suggests group-mediated interventions that support individuals' positive identification with the group are effective in promoting a range of positive health outcomes including psychological health and well-being (Steffens et al., 2019). Therefore, a group-mediated exercise intervention that focuses on harnessing the participants' social identities could support university students' exercise behaviour and well-being.

Due to the pandemic, there have been various physical distancing protocols set in place such as the moving university classes to on-line platforms. Therefore, there has been diminished opportunities for university students to socially connect with one another. Physical distancing protocols have also put restrictions on recreational centers and programs that provide students opportunities to engage in exercise and socially connect with one another. Therefore, the use of 'virtual running groups' is one way to provide individuals, such as university students, with necessary physical activity and social connectivity during the pandemic. Walking and running are two of the most common forms of physical activity participated in by those living in North America (e.g., Canada, United States) (Hulteen et al., 2017), and is an activity that can be done in one's own residential area whilst following Covid-19 physical distancing protocols.

**Aims:** Given the proposed study is a pilot trial, the main purpose is to assess whether the intervention is feasible, and determine participants' acceptance of the program. Various markers of program feasibility and acceptability will be assessed, such as (a) university students' interest in the program, and feasibility of recruitment, (b) participant satisfaction with virtual running groups, (c) affective attitudes towards exercising, (d) participant adherence to the program and control condition, (e) participation rates of group activities, (f) completion rates of assessments, and (g) participants' perception of whether a virtual running group provided adequate social connection.

Although formal hypothesis testing of efficacy is ill-advised in pilot studies given their lack of power (Eldridge et al., 2016), we will examine secondary outcomes that have theoretical and practical importance for exploratory purposes, and calculate statistical information such as effect sizes and measurement variance for informing power analyses when planning future efficacy trials. The secondary outcomes include changes in perception of social support in the context of exercise, global well-being (i.e., flourishing), exercise related well-being (i.e., subjective vitality), exercise identity, and exercise behaviour. Participants' ratings of social identification with their running group will also be assessed at the end of the program (Week 8).

**Research Design:** The study will utilize a two-arm, parallel group, unblinded randomized controlled pilot trial design. UBC undergraduate students ( $N = 60$ ) will be equally randomized to either an eight-week social identity building virtual running group ( $n = 30$ ) or an eight-week control group ( $n = 30$ ). The group component of the intervention will be delivered via Zoom to support social connection among running group members and the fitness/social media app Strava so participants can post their runs and walks for members of their running group to view and provide words of encouragement. The virtual component is utilized to adhere to physical distancing protocols associated with the current COVID-19 pandemic. The attention control group will receive information regarding physical activity guidelines, be encouraged to meet the Canadian physical activity guidelines, and be asked to record their runs and walks on Strava. The use of an attention control condition will enable us to control for any potential effect of tracking exercise on outcomes such as well-being, exercise identity, and exercise behaviour.

**Study Population:** The target population are UBC undergraduate students (18+ years and enrolled in part time or full time studies) that have been underactive (i.e., not meeting the Canadian guidelines of 150 minutes of moderate-to-vigorous exercise per week) in the past month. Participants must be able to speak and read English, be living in Canada, and not experience any health contraindication that might prevent that person from participating in moderate-to-vigorous intensity exercise. Participants must own a smartphone so they can record their runs and walks on Strava, and have access to the internet and own a device that has camera functionality (e.g., computer) for attending the virtual coffee chats hosted on Zoom.

**Recruitment:** Sixty UBC undergraduate students will be recruited using online tools such as social media (Facebook, Twitter, YouTube, and Instagram), announcements in UBC online undergraduate classes, and different UBC outlets (e.g., UBC Wellbeing, UBC Recreation, The Ubyssey) will be asked to advertise the study on their media outlets (e.g., newsletters, social media). Students interested in participating will be asked to contact the student investigator directly via email ([[contact]](mailto:[contact])). Once individuals express interest, the student investigator ([name]) will provide potential study participants with the study information letter so that they can see what the study entails, and schedule the best time to conduct the screening interview. At that time, eligibility will be assessed and confirmed. The student investigator will reaffirm the information about the study (provided in the information letter).

Upon agreement, the student investigator will obtain consent from participants (via Qualtrics) and direct participants to complete the baseline questionnaire (again, via Qualtrics). Once completed, the student investigator will contact the participant to inform them which intervention

group they are in by phone and email. Participants in the intervention condition will be directed to the UBC Canvas portfolio and asked to attend the first meet-and-greet meeting facilitated by the student investigator. During the meet-and-greet, participants will be (a) introduced to the Canvas materials that facilitate their participation in the running group, (b) provided instruction for Strava use, (c) provided information about the group goal, (d) provided explanation of the weekly structure of the program, (e) provided running and exercise considerations (hydration, nutrition, warm-up, safety, footwear and clothing, running pacing), as well as instructed to inform their physician if they experience negative symptoms when exercising (e.g., difficulty breathing) (f) asked to introduce themselves to their running group and brainstorm a team name. The Canvas website will include (a) information about the study (e.g., group goal explanation, Strava instructions), (b) a weekly video providing tips on running (from YouTube), (c) a videoconferencing link for the weekly coffee chats, and (d) discussion questions for the weekly coffee chat. The student investigator will coordinate the completion of the baseline and post-intervention surveys, as well as weekly exercise logs.

We will use a rolling recruitment strategy. As soon as the first 12 participants are recruited, they will be randomized to the virtual running group program or the control group, and begin participation (i.e., cohort 1). If more than 12 participants are recruited (e.g., 24 participants), then 2 cohorts will be created and will begin participating at the same time. Therefore, multiple cohorts will likely begin participation in the study at different time points. We will aim for five cohorts in total (N = 60).

**Randomization:** Once participants complete the baseline questionnaire, they will be randomized to the intervention group (n = 30) or the control group (n = 30) using a random number generator. We aim for 50% recruitment of men and 50% recruitment of women. We will stratify to ensure equal distribution of men and women across conditions. Sequence generation will be completed separately for men and women using the randomizer.org tool for researchers, with blocks of 2 unique numbers (1, 2) with each number designating one of the two randomization groups. Participants will be randomized in the order they complete the baseline survey.

**Assessment and remuneration:** Participants in both conditions will be provided with \$10 for completing the baseline survey, and \$10 for completing a post-intervention survey. Participants who complete 100% of the weekly exercise logs will receive \$15, and participants who complete at least 75% (i.e., 6-7 logs) of the logs will receive 10\$. Participants in the virtual running group program (n = 10) will be asked to complete a post-intervention semi-structured interview, with the student investigator, assessing their experiences with the STRIDE program. If more than 10 participants indicate interest in participating in the interview, we will select those to be interviewed by a random draw. Interviews will be conducted via Zoom (although only the audio component of the conversation will be recorded). Participants who complete the interview will be provided \$20 for their time.

**Virtual Running Group Condition:** Participants in the virtual running group will be placed into running groups of six people. Each running group will be given the group goal/challenge to collectively run/brisk walk the distance across the province of British Columbia (i.e., from UBC to BC/Alberta Border), for a total distance of 940 kilometers. Individuals have the choice to determine how they will contribute to the collective goal. On average, if each individual were to

complete 20 km a week ((20 kilometers \*6 individual)\*(8 weeks)), that would equal 960 kilometers traveled for the total group across eight weeks. The group running program refers to the shared activity approach in social identity building interventions (Steffens et al., 2019), whereby each individual in the group simultaneously runs/walks, and interdependently work together to achieve the collective goal of running 940 km. The collective goal will be implemented with the purpose of providing members with a shared sense of 'we' and 'us', a common purpose and meaning behind group activity, and will help establish the running group as a distinct group (Levy et al., 2018).

Each participant will be encouraged to complete 150 minutes of moderate-to-vigorous exercise per week. Participants will be asked to record their runs and walks on the fitness application Strava. Participants will also be provided with phone armbands so that they can carry their smart phone on runs/walks. Running groups will be created on Strava so that individuals can post their runs/walks for their running group to view, and post words of congratulations and encouragement on each individuals' run/walk. In line with the Walk Kansas program (Estabrooks et al., 2008) participants can record leisure time moderate-to-vigorous exercise, such as strength training or recreational sport, to contribute to the group goal. In order to record an activity, it has to occur for at least 10 minutes. Leisure time exercise behaviour will be converted to kilometers traveled using Ainsworth et al.'s (2011) compendium of physical activities.

At the end of each week of the program, participants in the virtual running group program will have a coffee chat (via Zoom) to discuss their experience running in the previous week and discuss progress and challenges associated with meeting the group goal. Due to the rolling recruitment strategies, separate running groups may have coffee chats that overlap. The student investigator will create separate breakout rooms on Zoom for the separate running groups (6 individuals per group) if the coffee chat occurs at the same time.

Discussion questions will be implemented to stimulate group discussion about how the group and each individual member will work towards completing the group goal. Providing group members the opportunity to decide how they will contribute to the collective goal utilizes the group relevant decision-making strategy of social identity building interventions (Steffens et al., 2019). The weekly coffee chats are being implemented to provide group members the opportunity to socially connect, and discuss their experiences running. Participants will also be provided with t-shirts with the study logo in order to further establish a sense of 'us' and group identity.

**Control Condition:** Participants in the control condition will be asked to download the fitness application Strava to their smartphone, and track all of their runs and walks on Strava. Similar to the intervention group, participants will be provided with phone armbands to carry their phone during a run or walk so they can record the run or walk on Strava, and will be asked to try participating in 150 minutes of moderate-to-vigorous exercise per week.

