### **Exercise Behaviour**

Participant will report their moderate-to-vigorous exercise minutes per week (over the past month) using a modified version of the Godin leisure time exercise questionnaire (Courneya et al., 2004; Godin & Shephard, 1985).

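### Baseline is taken at individual consent but a cohort starts only at 12 recruits, leaving an unrecorded, variable wait inside the baseline-to-Week 8 interval

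*Combined protocol and SAP*

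**What the plan says.** The protocol's Recruitment section describes a person-by-person sequence of screening interview, consent and baseline: "Upon agreement, the student investigator will obtain consent from participants (via Qualtrics) and direct participants to complete the baseline questionnaire". The next step is notice of allocation: "Once completed, the student investigator will contact the participant to inform them which intervention" group they are in.

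The rolling-recruitment paragraph of the same section sets a cohort trigger: "As soon as the first 12 participants are recruited, they will be randomized to the virtual running group program or the control group", after which they begin. Five cohorts are planned, for a total of 60. If 24 are recruited, two cohorts start together.

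The Randomization section says "Once participants complete the baseline questionnaire, they will be randomized to the intervention group" or the control group, and adds: "Participants will be randomized in the order they complete the baseline survey". Allocation uses blocks of 2, separately for men and women.

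Under Exercise Behaviour, the recall window is the past month: "Participant will report their moderate-to-vigorous exercise minutes per week (over the past month"). Data Collection places the post-intervention survey at Week 8. The Analysis Plan uses 2 x 2 mixed ANOVAs and reports effect sizes for the between, within and interaction effects, with no term for cohort or for time since baseline. The Aims section says that effect sizes and variances are to inform power analyses for later trials.

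No section caps or records the time from baseline to cohort start, or repeats the baseline survey at the start.

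**The concern.** The secondary outcomes, and affective attitudes among the primary outcomes, are changes over an eight-week programme. If baseline is fixed at consent and the programme starts only when 12 places are filled, the measured interval is eight weeks plus a wait that differs from person to person. Three things are then at stake.

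- **Within-arm time effect.** Whatever changes during the wait (season, term, pandemic rules) is counted as change over the programme.
- **Variance for planning.** A longer and uneven gap can weaken the correlation between baseline and Week 8, which raises the change-score variance that the pilot is meant to supply.
- **Exercise baseline.** A past-month report made several weeks before the start no longer describes the month before the programme.

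The order of allocation adds a further question. If people are randomised and told their arm when they finish their own survey, someone who loses interest before the group forms is a post-randomisation loss, and retention is a primary feasibility outcome.

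**Working it through.** **Plan's own figure.** 5 cohorts x 12 = 60, and 5 running groups x 6 = 30 per arm. Both agree with the stated N. The documents give no power calculation and no accrual rate, so the accrual rates below are assumptions.

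**Length of the wait.** Assume steady accrual of r people per week, each cohort filling in turn, and Week 8 counted from cohort start. The i-th of 12 recruits waits (12 - i)/r weeks. The maximum is 11/r and the mean is 5.5/r. The mean baseline-to-Week 8 interval is 8 + 5.5/r. Taking a month as 4 weeks, the past-month report lies wholly before the final pre-start month when (12 - i)/r is at least 4, that is, when i is at most 12 - 4r.

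| Recruits per week | Mean wait (weeks) | Maximum wait (weeks) | Mean interval (weeks) | Wait as share of mean interval | Recruits of 12 with no overlap |
|---|---|---|---|---|---|
| 12 | 0.46 | 0.92 | 8.46 | 5% | 0 |
| 6 | 0.92 | 1.83 | 8.92 | 10% | 0 |
| 3 | 1.83 | 3.67 | 9.83 | 19% | 0 |
| 2 | 2.75 | 5.5 | 10.75 | 26% | 4 |
| 1 | 5.5 | 11 | 13.5 | 41% | 8 |

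**Balance between arms.** A simulation of five cohorts of 12 (20,000 repetitions, each recruit equally likely to be a man or a woman, blocks of 2 within sex, allocation in order of baseline) gave a between-arm difference in mean wait centred on 0. Its SD was 0.24 weeks at 3 recruits per week and 0.73 weeks at 1 per week. Any one trial may show a small chance imbalance, but there is no systematic one.

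**Effect on variance (illustration only).** With equal variances at both times, scaled to 1, the change score has variance 2(1 - r), where r is now the baseline-to-Week 8 correlation. If the wait lowered r from 0.7 to 0.6, this would go from 2 x 0.3 = 0.6 to 2 x 0.4 = 0.8, a rise of 33%. Neither correlation is in the documents. With two time points, the ANOVA interaction is a comparison of change scores, so this is the relevant variance.

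**When allocation happens.** The texts allow two orders.

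- *At individual baseline completion:* the Randomization sentence and the notice that follows the completed survey point this way. The wait then falls after randomisation.
- *At the twelfth recruit:* the rolling-recruitment sentence says "they will be randomized to the virtual running group program or the control group, and begin participation (i.e., cohort 1"). The wait then falls before randomisation.

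**Effect on retention.** Let q be the fraction lost in the wait and p the fraction of starters retained. Retention is (1 - q)p of those randomised under the first order, and p of starters. With assumed q = 0.10 and p = 0.90, that is 0.90 x 0.90 = 81% against 90%. With q = 0.20, it is 0.80 x 0.90 = 72% against 90%. Under the second order, the same losses precede randomisation. They would enter only if the percentages were taken over everyone enrolled, and the Retention section names no denominator.

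**The case against.** The strongest reply is that the trial has a concurrent randomised control. Both arms of a cohort start together, and blocks of 2 in order of survey completion tend to split neighbouring enrollees, who have similar waits, between the arms. A reader might infer that the wait biases the group comparison. It does not in expectation, and this part of the objection stands in full.

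A reader might also infer that participants are told their arm at once, that controls begin tracking and exercising before their cohort starts, and that waiting losses are necessarily randomised non-completers. The documents do not establish any of these. The notice comes after the survey, with no time stated. No section has controls start ahead of their cohort. The Randomization sentence can be read as a precondition, giving one coherent order: baseline, 12 accrued, randomise, notify, begin. The retention effect is therefore conditional on the other reading.

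The size is also open. Accrual may be fast, and the plan foresees 24 recruits starting together. Most of the analyses affected are exploratory, and the Aims section disclaims formal efficacy testing. Loss while a group forms is itself useful feasibility information, although it is useful only if it can be told apart from loss during the programme.

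What the objection does not remove is the sequence itself. Survey at consent and start at 12 recruits produce a gap that is not limited, recorded or reported, and variances and within-arm effects are outputs that this pilot says it will pass on.

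**Conclusion.** The point holds in a limited form. As written, all but the last enrollee of each cohort have a wait of varying, unrecorded length between baseline and start. Completing the survey on the same day is the only exception. The consequences are contamination of the within-arm time effects by pre-programme change, possible inflation of change-score variance, and an out-of-date exercise baseline for early enrollees. The arm-by-time contrast remains unbiased in expectation.

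The size depends on assumed steady accrual. The wait is minor at 12 recruits per week (about half a week on average). At 1 per week it is substantial: 5.5 weeks on average, with 8 of 12 past-month reports ending at least four weeks before the start. The 33% variance figure only restates an assumed fall in correlation.

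The Recruitment and Randomization sections should be reconciled on when allocation and notice occur. Lower retention from waiting losses as post-randomisation losses follows only if allocation occurs at individual baseline completion. This is an inexpensive improvement to make before recruitment, and it does not invalidate the design.

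**What to change.** State one order in the Recruitment and Randomization sections:

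1. Screen and consent on a rolling basis.
2. When a cohort's 12 places are filled, send its members the baseline survey shortly before the start date.
3. Randomise, and notify participants, only after that survey.
4. Start both arms of the cohort together and count Week 8 from that date.

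Record the dates of baseline, randomisation and cohort start for each participant. Report losses before randomisation as recruitment losses, separately from retention after it.

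**Cost.** The wording of two sections changes, and an existing online survey goes out at a different time. Some consented students may not complete the later survey and must be replaced, which can delay a cohort. Rechecking the past-month activity criterion at that point is optional, since it could remove a few more people and add delay. If the survey cannot be moved, recording the three dates and reporting the wait is the minimum. It would show the size of the problem without removing it.

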### **Analysis Plan**

With respect to the primary feasibility and acceptability outcomes, frequency values will be calculated for adherence to the program, number of weekly physical activity logs completed, number of Zoom group meetings attended, and number of post-intervention surveys completed. Descriptive statistics (mean, variance), skewness, and kurtosis will be calculated for the affective attitude items and the one item assessing program satisfaction. Cronbach’s alpha will be calculated for the four affective attitude items. A 2 x 2 within and between subjects ANOVA will be conducted to examine intervention by time effects on affective attitudes towards exercise. Effect sizes ( $\eta^2$ ) will also be calculated for the between, within, and interaction effects.

The interviews with participants will be transcribed verbatim. The transcripts will be analyzed using thematic analysis. First, codes will be generated to identify content that is relevant to understanding participants’ experiences with the program and virtual running crew/group. Second, codes will be analyzed to produce higher order themes regarding participants’ experiences with the program and virtual running crew/group (Clarke & Braun, 2017).

With respect to exploratory analyses, descriptive statistics (mean, variance), skewness, kurtosis, and Cronbach's alpha will be calculated for each secondary outcome variable. Multiple 2 x 2 within and between subjects ANOVAs will be conducted to examine intervention by time effects on perceived social support, flourishing, exercise-related subjective vitality, exercise identity, and exercise behaviour. Effect sizes ( $\eta^2$ ) will also be calculated for the between, within, and interaction effects.

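### Randomization is stratified by gender but none of the six ANOVAs includes it, which can make the between-arm test, and the arm-by-time test if men and women change differently, somewhat conservative

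*Combined protocol and SAP*

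**What the plan says.** The Randomization section states "We will stratify to ensure equal distribution of men and women across conditions". Men and women have separate allocation sequences in blocks of two, and participants are allocated in the order in which they finish the baseline survey. The intended mix is given as an aim: "We aim for 50% recruitment of men and 50% recruitment of women". Data Collection lists gender among the baseline demographics.

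The Analysis Plan gives one model for affective attitudes: "A 2 x 2 within and between subjects ANOVA will be conducted to examine intervention by time effects on affective attitudes towards exercise". It gives the same model for the secondary outcomes: "Multiple 2 x 2 within and between subjects ANOVAs will be conducted to examine intervention by time effects on perceived social support, flourishing", followed by exercise-related vitality, exercise identity and exercise behaviour. That makes 1 + 5 = 6 ANOVAs, each with arm and time as the only factors. Eta-squared is to be reported for the between, within and interaction effects. No gender term, adjusted analysis or sensitivity analysis is described, and no reason for leaving gender out is given.

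The Aims section calls formal efficacy testing inadvisable in a pilot. It also says that effect sizes and measurement variance will feed the power analyses of later trials.

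**The concern.** Stratified allocation keeps the arms balanced on gender, so gender differences contribute almost nothing to the chance variation of the arm contrast. A model without gender still counts such differences as residual variation wherever they enter the error term. The estimated standard error then exceeds the true one, and the test is conservative.

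Two outputs are at stake. One is the F, p and partial eta-squared values for the arm effects. The other is the variance information, which the Aims section makes a product of this pilot. Gender is already collected, so the remedy costs almost nothing.

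**Working it through.** The documents state no alpha, SD, power or gender difference, so there is no precision figure to reproduce. N = 60 agrees with the recruitment arithmetic (5 cohorts x 12 = 60; 5 running groups x 6 = 30).

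**Inputs from the documents:** 30 per arm, 1:1 within gender, and an intended 50/50 mix, which gives 15 per arm-by-gender cell. There are two time points, and the models contain arm, time and arm-by-time.

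**Assumed inputs:**
- g, the gender difference in change, in within-gender SDs of change: 0.2, 0.5, 0.8.
- G, a gender gap constant over time, in within-gender SDs of the outcome: 0.8, 1.5.
- Pre-post correlation 0.6, two-sided 5% level, complete data, independent participants.

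**Step 1: arm-by-time, constant gap.** With two time points, the arm-by-time F test is the squared two-sample t test on change scores. A constant gap G cancels in the change score. In 20,000 simulated trials per setting, G = 0.8 and 1.5 with g = 0 gave an interval-width ratio (gender omitted / included) of 1.000. The null rejection rates without gender were 0.049 and 0.051.

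**Step 2: arm-by-time, unequal change.** Take the within-gender variance of change as 1. With gender in the model, the error mean square has 57 df and expectation 1. Without it, the error sum of squares also takes in the gender degree of freedom, whose expectation is 1 + 60 x g²/4 = 1 + 15g². The expected error mean square is then (57 + 1 + 15g²)/58, so

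SE ratio = sqrt[(58 + 15g²)/58].

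| g | error-variance ratio | SE ratio | type I error, gender omitted | type I error, gender included | power, omitted | power, included |
|---|---|---|---|---|---|---|
| 0.2 | 58.60/58 = 1.010 | 1.005 | 0.047 | 0.048 | 0.474 | 0.478 |
| 0.5 | 61.75/58 = 1.065 | 1.032 | 0.045 | 0.052 | 0.455 | 0.478 |
| 0.8 | 67.60/58 = 1.166 | 1.080 | 0.036 | 0.050 | 0.424 | 0.478 |

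The type I errors come from the simulation. Power is for an assumed arm effect of 0.5 SD of change. Allowing for 58 rather than 57 df in the t quantile, the interval-width ratios are 1.005, 1.031 and 1.079. At g = 0 the ratio is 1.000, so including gender costs nothing visible when it is irrelevant.

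**Step 3: between-arm effect.** This test works on each person's mean of the two time points, so a constant gap does not cancel. The within-gender variance of that mean is (1 + 0.6)/2 = 0.8, and the SE ratio is sqrt[(58 + 15 x G²/0.8)/58].
- G = 0.8: sqrt[(58 + 15 x 0.80)/58] = sqrt(70/58) = 1.10 (simulation 1.10).
- G = 1.5: sqrt[(58 + 15 x 2.8125)/58] = sqrt(100.19/58) = 1.31 (simulation 1.32).

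**Step 4: which reported quantities move.** Under exact balance, gender is orthogonal to arm. The arm-by-time estimate, its sum of squares and the total sum of squares are the same with or without gender. Classical eta-squared for the interaction (effect SS / total SS) is therefore unchanged. F, p and partial eta-squared use the error sum of squares and do change.

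**The case against.** A reader might infer that all six analyses keep gender variance in the arm-by-time error term, so that every interval is too wide and every effect size misstated. The documents do not support that. The within-subject design already removes any constant gender gap from the arm-by-time test, and nothing in the documents suggests that men and women will change by different amounts. The plan names no confidence intervals or error bars. It specifies eta-squared without saying that it means the partial form.

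The net direction of error is also open. Intervention participants work in interacting groups of six, which the same ANOVAs ignore. With an assumed intraclass correlation in the intervention arm only, the true SE exceeds the naive one by a factor of sqrt[(1 + 5 x ICC + 1)/2]. That is 1.02, 1.06 and 1.12 at ICC = 0.02, 0.05 and 0.10. An overall claim that precision is understated could therefore have the wrong sign.

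The harm to planning is partly inferred. The plan computes descriptive variances and does not say that an ANOVA residual will be the planning SD, or that a later trial will stratify by gender. The ANOVAs' stated purpose is the intervention-by-time effect, the secondary ones are exploratory, and no decision depends on a p-value.

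All of this stands, and it limits the importance of the point. It does not remove the mismatch. The between-arm effect is still reported with an eta-squared, and there a constant gap does enlarge the error term. Exact balance is also not assured: dropout can upset it, and a gender term would then adjust for the imbalance.

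**Conclusion.** The mismatch is real and minor. The models omit the one factor on which randomization is stratified. The consequence depends on the term:

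- **Arm-by-time:** no effect from a constant gender gap. If change differs by gender, the SE is about 0.5%, 3% or 8% too wide at assumed differences of 0.2, 0.5 or 0.8 SD, with type I error about 0.047, 0.045 or 0.036.
- **Between-arm:** SE ratio about 1.10 at an assumed constant gap of 0.8 SD and pre-post correlation of 0.6.
- **Planning variance:** if the change-score residual were used to plan a later gender-stratified and gender-adjusted trial, it would be about 1%, 6% or 17% too large at the same three differences in change.

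The gender differences are assumptions, since the documents give none. The figures also assume 15 per cell, complete data and no clustering by running group. They show that this one omission is neutral or conservative; they do not show that the analysis as a whole is. Severity is low, because the main purpose is feasibility and acceptability and formal efficacy testing is disclaimed.

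**What to change.** In the Analysis Plan, add gender to each of the six models as a between-subjects factor, with its main effect and its gender-by-time term, and no interaction of gender with arm. Report the gender-adjusted arm and arm-by-time effects. State whether eta-squared is classical or partial. Report the gender-adjusted residual SD alongside the raw variance, so that whoever plans a later trial can choose the value that fits its design. If gender is to stay out of the models, give the reason.

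The cost is a sentence or two of text and one error degree of freedom (58 to 57). No new data are needed.
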